6.7.5 Physical examination

General physical examination data will be tabulated and listed. The summary table will include number/percentage of patients with normal or abnormal observations and NCS/CS frequencies/percentages for abnormal observations.

6.7.6 Dialysis regimen

Dialysis regimen data will be listed.

6.8 Scheduled visits, Dosing and Treatment Compliance

6.8.1 Visit dates

A listing with actual visit dates (and times, if applicable) per patient will be presented.

6.8.2 Dosing and Treatment compliance

Relevant dosing information, scheduled and actual dosing dates/times (if available) and treatment compliance information will be listed for each patient. Compliance will be determined using the drug accountability information collected in the database. The total number of capsules dispensed minus the total number of capsules returned is considered the actual amount of trial medication taken. This should automatically include the number of missed doses and possible fluctuations in the number of capsules per vial. The duration between the date of treatment start and the stop date of study medicine is considered the period over which the study medication has been taken. The theoretical amount of trial medication would then be the duration times 2, considering there is a morning and evening dose. Percentage compliance is then calculated as (actual/theoretical) *100% and will be added to the listing.

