6 INVESTIGATIONAL PLAN

6.1 Overall study design and plan

This study is an open label multi-centre study to evaluate the efficacy and safety of OC5 (*O. formigenes*) to reduce plasma oxalate in PH patients on dialysis. It is hypothesised that daily administration of *O. formigenes* facilitates the secretion of endogenously produced oxalate from plasma to the GI tract. The enteric elimination of oxalate in addition to dialysis may help to lower the build-up of extra-renal oxalate in PH patients in ESRD.

Patients will initially be treated for 6 weeks with OC5. The study patients will be monitored for 4 weeks prior to initiation of study medication, as well as 4 weeks of follow-up after termination of study medication. If the patient, in the opinion of the responsible investigator, has a positive effect of the study drug, patients will be offered to continue treatment with study drug after the 4-week follow-up period until transplantation (maximum length of the continued treatment period will be 36 months).

The investigator should confirm that the benefit/risk assessment for the individual patient is considered to be positive and that there are no complications or adverse events that could adversely affect the benefit/risk ratio. A repeated benefit/risk

assessment for the patient will be done and documented every three months throughout the continued treatment period.

Following screening and baseline evaluations eligible patients will receive Oxabact® twice daily for 6 weeks. The dose will be administrated orally with meals as one enteric-coated capsule two times per day preferably with breakfast and dinner. For patients using a gastric tube the capsules may be administered through the tube. The dose will be NLT 1E+09 CFU/capsule.

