6.2.4 Post treatment period – 4 weeks without study drug (study week 11-14)

During the post-treatment period study visits will take place at week 12 and 14. A blood sample will be taken for determination of plasma oxalate prior to the dialysis session in week 12 and 14.

At week 14 faecal sample will be taken as well as safety labs.

At each clinic visit the patient will be assessed for the presence or absence of Adverse Events and changes in concomitant medications. At the clinical visit week 14 a physical examination including vital signs will be performed.

Adverse Drug Reactions (i.e. AEs that are possibly or probably related to study treatment, see section 11.1), which are unresolved at the time of week 14 clinic visit, should be followed until the event has resolved or, if persistent, has been assessed as “chronic” or “stable” for patients not participating in the continued treatment period.

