6.6.2 Secondary endpoint

All secondary endpoint analyses will be performed for the FAS only, unless specifically stated that mFAS will also be used. All secondary endpoint analyses will be done on the overall treatment period, unless otherwise specified.

Free plasma oxalate

Change in free plasma oxalate level during OC5 treatment will be analyzed descriptively (tables and plots) as described for the primary endpoint.

Total and free plasma oxalate levels from week 10 to week 14

After 6 weeks of treatment, there is a 4 week off-treatment period scheduled. Change in total and free plasma oxalate levels following the 4 week off-treatment at week 12 and 14 will be calculated as the value at visit 12 or 14 minus the visit value at week 10. Summary statistics of the measurements will be presented on a per-visit basis. Both the actual value as well as the change from baseline value will be presented for the FAS. For handling missing data in summary statistics for CFB values, see section [6.2](#).

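### Read literally, the compliance formula in SAP 6.8.2 counts the planned four drug-free weeks, so fully adherent patients who enter continued treatment are listed below 100%

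*SAP*

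**What the plan says.** SAP section 6.8.2 gives the calculation in four steps.

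- Numerator: "The total number of capsules dispensed minus the total number of capsules returned is considered the actual amount of trial medication taken".
- Period: "The duration between the date of treatment start and the stop date of study medicine is considered the period" of drug intake.
- Denominator: "The theoretical amount of trial medication would then be the duration times 2, considering there is a morning and evening dose".
- Result: "Percentage compliance is then calculated as (actual/theoretical) *100% and will be added to the listing".

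There is one capsule total, one start date, one stop date and one duration. Nothing is deducted for time off drug, and no calculation by treatment phase is described.

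The design interrupts treatment on purpose. Protocol section 6.1 says "Patients will initially be treated for 6 weeks with OC5". Protocol section 6.2.4 then sets study weeks 11 to 14 as a period without drug, and SAP section 6.6.2 confirms that after those six weeks "there is a 4 week off-treatment period scheduled". The schedule in SAP section 2.5 (Table 1) shows no treatment in those weeks. CT follows for some patients, for at most 36 months, with the last visit at CT week 156. A footnote to the CT schedule (SAP Table 2) says that the first CT visit may fall together with the week 14 visit, so CT can also begin later.

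**The concern.** For a patient who enters CT, the interval from treatment start to the stop of study drug spans the off-treatment weeks. The formula then expects two capsules a day on days when the protocol gives none. Even perfect adherence cannot reach 100%, and the shortfall depends on how long the patient stayed in CT rather than on how many doses were missed.

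This percentage is the only derived adherence measure in the SAP. Protocol section 12.1 builds the efficacy evidence from individual cases read together, so someone studying one patient's oxalate course may well look up that patient's compliance. According to Protocol section 11.5.1.2, 8 of the 12 treated patients entered CT, so the distortion would touch most of the study population and leave the other four untouched.

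**Working it through.** The documents state no compliance result, so there is no figure to reproduce. The check applies the formula in SAP 6.8.2 to a patient who takes every capsule.

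**Inputs**

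- Initial dosing: 6 weeks = 42 days (Protocol 6.1).
- Planned time off drug: 4 weeks = 28 days (Protocol 6.2.4; SAP 6.6.2).
- Dose frequency: 2 capsules a day (Protocol 8.1; SAP 6.8.2).
- CT length: C days, up to 156 × 7 = 1092.
- Assumptions: days are counted inclusively, and CT starts straight after week 14, so the gap g is 28 days.

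**Formulas**

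- Capsules taken = 2 × (42 + C).
- Theoretical amount as written = 2 × (42 + g + C).
- Listed compliance = 100 × (42 + C) / (42 + g + C).
- Capsules counted but never due = 2g = 2 × 28 = 56, whatever the CT length.

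**Results for full adherence, g = 28**

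| CT length | Taken | Theoretical as written | Listed | With off-drug days removed |
|---|---|---|---|---|
| None (g = 0) | 84 | 84 | 100.0% | 100.0% |
| 4 weeks | 140 | 196 | 71.4% | 100.0% |
| 24 weeks | 420 | 476 | 88.2% | 100.0% |
| 52 weeks | 812 | 868 | 93.5% | 100.0% |
| 104 weeks | 1540 | 1596 | 96.5% | 100.0% |
| 156 weeks | 2268 | 2324 | 97.6% | 100.0% |

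**Comparability.** A fully adherent patient with 4 weeks of CT is listed at 71.4%. A non-continuer who missed 24 of 84 capsules gets the same figure: 60/84 = 71.4%.

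**Sensitivity to the day count.** The SAP does not say whether the duration includes both end days. If it is stop minus start, the denominator falls by 2 capsules: 140/194 = 72.2% at 4 weeks, 812/866 = 93.8% at 52 weeks and 2268/2322 = 97.7% at 156 weeks. A fully adherent non-continuer would then show 84/82 = 102.4%.

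**Sensitivity to a late CT start.** With assumed gaps of 42 or 56 days, the listed figure is 90.6% or 87.9% at CT week 52, and 96.4% or 95.3% at CT week 156.

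**The case against.** The strongest reply is that little depends on this number. The full analysis set, the modified set and the safety population require only a dose received (SAP 3.1). No table in SAP 10.3 shows compliance; it appears in listing 16.2.5.1. Dosing dates (where available), drug accountability and visit dates are also listed, so a careful reader could see the gap and recompute. All of this stands, and it sets the severity.

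A second reply is that the SAP does not specify the first start or the last stop. It describes a period in which drug was taken, which the off-treatment weeks are not, and SAP 2.2 separates the initial phase from CT. A programmer could therefore apply the formula phase by phase. That reading is possible, but it is less natural: the capsule count is a single total, and the SAP names periods elsewhere when it wants results by period. If two programmers can reach different numbers, the text still needs correcting.

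A third reply is that the low percentages may describe few patients. SAP 2.4 and 6.3 plan for at least 6 patients to complete CT week 52 and base the first interim analysis on them; SAP section 7 refers to that interim as done. If it followed the plan, at least 6 of the 8 continuers reached week 52, and with a 28-day gap their shortfall is at most 100 − 93.5 = 6.5 points. Larger errors could then affect at most two patients, and the documents do not show that anyone stopped at 4 weeks. This stands too.

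The numerator is also approximate, because capsules lost or not returned count as taken. That is a separate limitation and does not justify a denominator containing capsules that were never due.

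A reader might go further and infer that adherent patients would be classed as non-compliant, or that false protocol deviations would follow. The documents support neither. They contain no compliance threshold or category, and deviations are identified by those responsible for data collection and compliance, then reviewed before database lock (SAP section 4). Nothing ties them to this percentage.

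**Conclusion.** Wrong as written; low severity. Followed literally, SAP 6.8.2 gives too low a percentage for every patient who enters CT, because at least 56 capsules in the denominator were never scheduled. The understatement for a fully adherent patient runs from 28.6 points at 4 weeks of CT, through 11.8 at 24 weeks and 6.5 at 52 weeks, to 2.4 at 156 weeks. It is larger if CT began after week 14, and absent for patients who did not continue. The listed percentages are therefore not comparable between patients.

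These sizes rest on the single-interval reading, inclusive days, a 28-day gap and full adherence. No efficacy result, safety result or analysis set changes.

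**What to change.** In SAP 6.8.2, define two dosing periods: the initial six-week period, and CT from its first to its last dosing day. For each, set the theoretical amount to (stop − start + 1) × 2. Report compliance for each period. Report the overall figure as capsules taken summed over both periods, divided by capsules due summed over both periods. A fully adherent patient then shows 812/812 at CT week 52 and 2268/2268 at CT week 156, that is 100%.

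The numerator can be split in the same way, since Protocol 8.3 has unused drug from the initial period returned by week 12, before CT begins. If the database lacks a separate stop date for the initial period or start date for CT, the SAP should say which dates stand in for them.

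The cost is a few sentences in the SAP and a small change to one derivation. No dosing or clinical rule is touched, and no new data are needed provided those dates were recorded.

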7 CHANGES TO PROTOCOL OR OTHER RELEVANT REMARKS

The change from baseline in total:free plasma oxalate level during OC5 treatment was previously added as additional secondary endpoint (being considered a post-hoc analysis as the endpoint was not mentioned in the protocol) and was evaluated during the first interim analysis. It has been removed for the final analysis.

The wording “pre-dialysis” has been removed from all endpoints upon request of Sponsor, to avoid confusion with the terminology.

An additional STE parameter was added, to be calculated based on other parameters. This additional parameter was first called Apical Sparing Patterns (and was presented as such in the first interim) and was later renamed to Relative Apical Longitudinal Strain (abbreviated as RALS).

For the first interim analysis, STE parameters Global Radial Peak Systolic Strain and Global Circumferential Peak Systolic Strain have also been presented until 52 weeks, however following a previous protocol update, these parameters are removed from CRF and database.

AEs after last dose date, and thus also after study drop-out, are not collected. As a consequence, TEAE after last dose date will not be present.

The in/exclusion criteria for the centers in Germany and France are different, as expressed by the latest blank CRF. Furthermore, there are some slight differences in criteria descriptions depending upon the protocol version used. For the listings, the results as presented in the database will be used.

8 DATA RECEIPT

All clinical data will be received as SAS files from the Data Management provider as agreed and will be transferred to SDTM format for the final analysis. The information regarding protocol deviations will be received as excel file (a so-called “protocol deviations log”) and will be transferred to SDTM. The SDTM files will be recoded to ADaM format. Listings will be programmed on the SDTM and, if necessary, ADaM datasets. Tables and figures will be programmed on ADaM datasets. Only necessary adaptations, not being able to be handled on database level, will be described in NTFs and used for adaptations in the ADaM datasets and included in the applicable ADaM documentation.

Interim analyses will be programmed using raw SAS data or derived datasets instead of SDTM/ADaM datasets, considering that unclean data will cause errors in the CDISC formats.

9 TECHNICAL DETAILS

9.1 Programming conventions

In the database, the variable ETHNIC is collected. However, following SDTM, its contents are more in line with what should have been collected as RACE. Therefore, we convert this variable to race, and program ethnicity as UNKNOWN.

Due to a systematic error in molarity values reported, the values for total plasma oxalate need to be converted by multiplying the received values by a factor of 0.71. This will be done for all listings, tables and graphs displayed for the study.

O.formigenes (genotype 1, genotype 2 and sum of genotypes) counts will be reported in $\times 10^6$. Data collected for *O.formigenes* in faeces will only have measurable values if above the LOD. Values below the LOD will be reported as 0 in the dataset. These values will be replaced with $LOD/\sqrt{2}$ for calculation purposes in descriptive statistics, plots and statistical analyses, only when there is a limited amount of data $< LOD$ present. The LOD values used are 118.000 ($0,118 \times 10^6$) for genotype1 and 37.900 ($0,0379 \times 10^6$) for genotype2. Note that in case of a

provided value lower than the LOD, it will be presented and used as is and not replaced with the LOD value.

BMI will be calculated in SAS as follows: weight/height², with weight in kg and height in meter (unit kg/m²).

For STE and TE parameters, a value of -99 in the database indicates that the value is missing, and these values will be treated accordingly.

Relative Apical Longitudinal Strain (in STE data) will be added to the analysis. Relative Apical Longitudinal Strain (LS) is calculated as: RALS = Avg. apical LS / (Avg. basal LS + Avg. mid LS).

Durations, determination of baseline values and handling of missing data will be programmed as stated in the respective analysis sections.

Study day will be added to some of the listings and calculated as follows: if the study date is before the date of first study dosing, then study day = first dose date – collection date. If the study date is after first dosing, then study day = collection date – first dose date +1. Time will be no factor in the calculation. If the study date is (partly) missing, and study date is before first dose date, then the first day of the month, and/or the first month of the year will be used. If collection date is completely missing, then study day cannot be determined.

It may be necessary to convert safety laboratory parameters to standardized units when lab measurements are provided in different units. Conversion factors and number of decimals for standardized values used will be supplied or approved by sponsor.

Any other programming conventions that are not foreseen in preparation of this SAP, will be handled when encountered and documented separately.

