6.2.2 Baseline

During baseline plasma oxalate sampling will be done at week 2 and 4. The blood sample will be taken after two consecutive days of dialysis on the preceding days, but prior to the dialysis session on the day of sampling. The blood sample will be processed at the clinical site and the acidified plasma will be shipped frozen to the central

laboratory (Academical Medical Center, Amsterdam, The Netherlands) for determination of oxalate using the Isotope dilution Gas Chromatography with mass selective detection (GC-MSD). Plasma oxalate will also be determined using the Ion Chromatography method at Bonn University Clinical laboratory, Germany.

Safety labs and faecal testing for *O. formigenes* will be performed in week 4.

The faeces sample will be collected either at patient's home or at the clinic and shipped for analysis at Institut für Mikroökologie, Herborn, Germany.

Any changes in concomitant medication will be recorded in the CRF at visit week 2 and 4. At week 4 each patient's eligibility will be reviewed to assure that no exclusionary conditions have developed since the screening visit. The result from the week 2 plasma oxalate sample (total plasma oxalate) will be reviewed for patient eligibility at this point.

For patients who fail any of the inclusion or exclusion criteria, applicable parts of the CRF should be completed and they should be recorded as screening failures in the Screening and Inclusion log.

After verification of the inclusion and exclusion criteria, the patient will be included in the study to receive study treatment.

At the clinical visit week 4 the patient and/or the parents will be instructed about the administration procedures for the study drug. See section 8.1 regarding dose administration. The patient will be scheduled for clinic visits at week 6, 8, 10, 12 and week 14.

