7 SELECTION AND WITHDRAWAL OF PATIENTS

7.1 Patient inclusion criteria

1. Signed informed consent (as applicable for the age of the patient). An appendix to the informed consent form will be signed by patients continuing on treatment after week 14.
2. Male or female patients \geq 2 years of age. Patients have to be able to swallow size 4 capsules twice daily, or use a gastric tube that allows for administration of size 4 capsules.
3. A diagnosis of PH (as determined by standard diagnostic methods).
4. Patient should be on a stable dialysis regimen for at least two weeks before baseline.
5. Plasma oxalate \geq 40 micromole/L prior to the dialysis session.
6. Patients receiving vitamin B6 must be receiving a stable dose for at least 3 months prior to screening and must remain on the stable dose during the study. Patients not receiving vitamin B6 at study entry must be willing to refrain from initiating vitamin B6 during study participation.

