4 BLIND DATA REVIEW MEETING

Protocol deviations will be identified to the extent possible by individuals responsible for data collection/compliance, and its analysis and interpretation.

Prior to database lock, the protocol deviations will be discussed during the (Blind) Data Review Meeting (BDRM). Invitees to this meeting are the OxThera Chief Medical Officer (CMO), the OxThera Statistician, the OxThera Project Manager (PM), the PSR Lead Data Manager (DM) and the AUTHOR! (Lead) Statistician, but more roles can be invited if considered necessary. Input to this meeting will be supplied by PSR PM/Data Management at least one week in advance of the meeting along with all protocol deviations identified during the study to the extent possible by individuals responsible for data collection/compliance, and its analysis and interpretation. The meeting is intended to resolve any outstanding data cleaning issues and consider the impact of certain protocol deviations on statistical analyses. Protocol deviations will be classified as important or not important.

The decisions taken during the meeting will be documented by the PM (or a delegate as agreed) and sent for review to all parties involved as soon as possible after the meeting, but before database lock. If all parties involved agree, then the document is finalized, signed by all attendees, and stored before database lock by the PM.

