6.4 Subject and study disposition

6.4.1 Inclusion/exclusion criteria

An individual patient listing of the deviations from inclusion and exclusion criteria will be presented. Eligibility information is collected at screening and at week 4 and will therefore be presented per visit in the listings.

It should be noted that the CRF and thus the database for inclusion/exclusion criteria differs between centers. This may lead to separate listings per center.

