6.4.4 Protocol Deviations

All protocol deviations will be listed including classification of importance as agreed prior to database lock.

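### Does converting total plasma oxalate by 0.71 oblige the SAP to re-check the entry limit of 40 µmol/L?

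*SAP*

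**What the plan says.** The conversion stands in SAP 9.1: "the values for total plasma oxalate need to be converted by multiplying the received values by a factor of 0.71". It covers every listing, table and graph of the study.

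On entry, Protocol 7.1 criterion 5 requires plasma oxalate of at least "40 micromole/L prior to the dialysis session". The criterion names neither total nor free oxalate, nor a week. Protocol 6.2.2 adds, for the week 4 visit: "The result from the week 2 plasma oxalate sample (total plasma oxalate) will be reviewed for patient eligibility at this point".

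On reporting of eligibility, SAP 6.4.1 states: "An individual patient listing of the deviations from inclusion and exclusion criteria will be presented". SAP 7, after noting that the criteria differ between the German and French centres and vary with protocol version, says: "For the listings, the results as presented in the database will be used". On deviations, SAP 8 states: "The information regarding protocol deviations will be received as excel file". SAP 6.4.4 adds: "All protocol deviations will be listed including classification of importance as agreed prior to database lock". Before lock, the data review meeting of SAP 4 considers them: "Protocol deviations will be classified as important or not important".

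Under SAP 3.1.1 the full analysis set (FAS) takes in everyone dosed at least once, whether or not the entry criteria were met.

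**The concern.** The SAP corrects the primary endpoint variable but does not carry the correction back to the entry criterion that, in the current protocol text, is judged on the same analyte. Conversion happens at the programming stage, which suggests that the data as received still carry the error. If sites also judged eligibility on the uncorrected scale, the floor actually applied was well below 40.

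The deviation log and the eligibility listing both draw on what was recorded at the time. Neither would then show a criterion 5 entry for a patient whose corrected week 2 value is under 40. At stake would be the description of the enrolled population and the completeness of deviation reporting.

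**Working it through.** The plan states no figure of its own to reproduce: the sample size is not power-based, and no converted entry limit is given. Only direct arithmetic applies.

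**Inputs**
- Conversion factor: 0.71 (SAP 9.1).
- Entry limit: 40 µmol/L (Protocol 7.1, criterion 5).
- Treated patients: 12 (Protocol 4.4, Table 3; Protocol 11.5.1.2).
- Baseline oxalate values: not given.

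**Step 1. The limit on the corrected scale, if received values were used at entry**
- converted = 0.71 × received = 0.71 × 40 = 28.4 µmol/L
- shortfall = 40 − 28.4 = 11.6 µmol/L

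**Step 2. The received value needed for a corrected 40**
- 40 / 0.71 = 56.34 µmol/L
- check: 56.3 × 0.71 = 39.97 (below 40); 56.4 × 0.71 = 40.04 (not below)

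A received week 2 value from 40 to below 56.34 would therefore convert to 28.4 to below 40. For example, 50 becomes 35.5.

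**Step 3. If corrected values were used at entry**
- The limit stays at 40 and nobody is affected.

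**Step 4. What the 28.4 figure rests on.** It needs two facts that the documents do not supply.
- *Scale:* nothing says when the molarity error was found or which values the sites saw.
- *Assay and week:* the week 2 total-oxalate check in Protocol 6.2.2 is the current wording (version 12, October 2019). The study started in May 2014, and all 12 patients had been enrolled by September 2019. Criterion 5 itself is silent on assay, SAP 7 says criteria varied by country and protocol version, and Protocol 10.1 shows that some local free-oxalate results already existed as routine care before Amendment VII. So it is not established that every patient was admitted on week 2 total oxalate.

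The count affected is thus between 0 and 12.

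**Step 5. Does any result depend on it?**
- FAS membership depends on dosing, not on criterion 5, so the analysed patients are the same in every case.
- Baseline is the average of weeks 2 and 4 (SAP 6.1), taken from converted values, as are all later values. No analysis uses 40 as a cut-off.

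**Step 6. Would a low baseline stay hidden?**
- Table 14.2.1 gives actual total oxalate by visit (SAP 6.6.1), and SAP 6.1 includes the minimum and maximum among its summary statistics.
- Figures 14.2.5 and 14.2.8 show individual courses of actual values.
- Listing 16.2.6.1 gives each measurement.
- All of these carry the conversion, and SAP 6.1 has the original value shown next to a derived one in listings. The comparison with 40 can be read off for 12 patients.

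**The case for a change.** The best case for acting is that the check is cheap and the study is read patient by patient. Protocol 12.1 rests efficacy on individual cases taken together, so each patient's eligibility status matters to the reader. Anyone compiling the deviation log from unconverted values would see no breach. SAP 7, which collects changes and remarks, does not mention the conversion. A few lines of text and about 12 comparisons would settle the matter.

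Much of this stands as description: no planned eligibility or deviation output makes the link, and the arithmetic is exact. It would be good practice for the study report to say which assay and scale lay behind criterion 5.

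It does not amount to a defect in the plan. The SAP re-derives no entry criterion from the data; criterion 5 is handled like all the others. A patient whose reported result met the limit at the week 4 review was admitted in the way the protocol describes, and a later recalibration of the assay does not by itself make that a deviation. Whether it counts as one is a matter for the data review meeting, which exists for such questions and may bring in further roles. Nor does it follow that a reader would believe every patient was at 40 or above, since the corrected values themselves are what the report displays. That 28.4 lies below the 30–60 µmol/L saturation range in Protocol 4.1.2 adds nothing, because the protocol does not tie the entry limit to that range.

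**Conclusion.** No change to the plan follows. The gap is a missing cross-reference between two sets of outputs, and analysts and the data review meeting can close it from values already scheduled for reporting.

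In the worst case, with received week 2 total oxalate used for every patient, the entry limit corresponds to 28.4 µmol/L on the corrected scale, and patients with received values from 40 to below 56.34 sit under 40. If corrected values were used, the effect is nil. The documents do not say which case holds, so the number affected is unknown and may be zero.

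In either case enrolment is finished, the FAS is unchanged, the primary and secondary estimates are unchanged, and all evaluations are exploratory (SAP 6.1). The conclusion rests on SAP 9.1 being applied to all outputs, and on the individual oxalate listing being produced, as planned.
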